2.2 Analysis Populations

The statistical analyses will be performed based on the following four subject populations:

- Modified Intent-to-Treat efficacy population The modified Intention-to-treat (mITT) population includes all subjects who are randomized and dispensed the investigational product, and will be analyzed according to the randomization scheme; subjects with a photographic and categorical scale Month 1 assessment via a remote visit will be excluded from the mITT.
- Intention-to-treat efficacy population The Intention-to-treat (ITT) population includes all subjects who are randomized and dispensed the investigational product, and will be analyzed according to the randomization scheme.
- Per-protocol efficacy population The Per-protocol (PP) population is a subset of the mITT subjects who have no protocol deviations that are considered to have a substantial impact on the primary efficacy outcome.
- Safety population The safety population includes all subjects who were administered the study product and will be analyzed according to as-treated principle.

2.3 Study subjects

2.3.1 Subject disposition

Subject disposition will be presented by treatment group and overall. The number of subjects in each study population (i.e. mITT, ITT, PP and Safety) will be summarized. Study population variables will also be presented in a data listing. Study completion, as well as early discontinuation, will be described for all subjects as well as by visit and by center.

Reasons for early discontinuation will be summarized and listed. All withdrawn subjects will be listed individually, including at least subject number, date and reason for withdrawal, and last visit performed, along with the relevant comments recorded on the eCRF (i.e., the Exit Form).

Protocol deviations 2.3.2

A protocol deviation occurs when a subject deviates from the protocol procedures. Depending on the seriousness of the deviation, the subject might be excluded from the PP analysis. Since PP will be used for the primary analysis at Month 1 only, the focus will be on deviations occurring before and on Month 1 visit day, as they might compromise the primary endpoint.

Doc id 43QM1901 Statistical Analysis Plan US - QM1114-DP - LCL 🞝 GALDERMA MA-43263

Print date:

2021-04-15 15:20

For this study, the protocol deviations that will exclude subjects from PP are identified in (but not limited to) Table 2 below.

Table 2. Protocol deviations

| Deviation |
|--|
| Any subject that conducts their Month 1 visit out of window by |
| greater than 14 days or earlier than 7 days |
| Any subject not treated according to the assigned treatment |
| Any subject that does not complete the LCL-ILA at maximum |
| smile at the primary endpoint visit (Month 1) |
| Any subject that does not complete the LCL-SLA at maximum |
| smile at the primary endpoint visit (Month 1) |
| Any subject that does not have an available screening or baseline |
| LCL-ILA at maximum smile assessment |
| Any subject that does not have an available screening or baseline |
| LCL-SLA at maximum smile assessment |
| Any subject that does not have grade 2 or 3 at maximum smile on |
| the LCL-ILA at baseline |
| Any subject that do not have grade 2 or 3 at maximum smile on |
| the LCL-SLA at baseline |
| Any subject with prohibited concomitant treatments/procedures |
| prior to Month 1 visit considered to have a substantial impact on |
| the primary efficacy outcome. |
| Any subject with a prohibited medical history, unstable medical |
| history condition, or medical history condition that worsens prior |
| to Month 1 visit considered to have a substantial impact on the |
| primary efficacy outcome |

Before unblinding the subject data, and as a part of preparations for the database lock, the study team will review all protocol deviations. All protocol deviations will be presented in a data listing.

Handling of Protocol Deviations During COVID-19

Due to the public health emergency related to the COVID-19 pandemic during 2020, steps have been taken to ensure patient and practitioner safety in alignment with FDA Guidance dated May 11, 2020 (Guidance on Conduct of Clinical Trials of Medical Products during COVID-19 Public Health Emergency). Most notably, in partnership with clinical sites and the Institutional Review Board (IRB), optional remote assessment procedures for efficacy and safety endpoints have been implemented to ensure safety and respect localized and elective restrictions.

Protocol deviations will be presented descriptively, overall and by treatment group. The total number of deviations, the type of protocol deviation, and if the deviation was reportable to the IRB will be summarized. These summaries will be stratified by relatedness to COVID-19 (related, not related). The above summary of protocol deviations will be repeated by site as well.

A listing of all protocol deviations reported throughout the study, including their relatedness to COVID-19, will be provided.

Demographic characteristics 2.3.3

Demographic assessments for this study include:

- Age (years)
- Height (in)
- Weight (lbs.)

Print date:

2021-04-15 15:20

- BMI (kg/m²)
- Gender (Male, Female)
- Ethnicity (Hispanic or Latino, Not Hispanic or Latino)
- Race (White, Black or African American, Asian, American Indian or Alaska Native, Native Hawaiian or Other Pacific Islander, Other)
- FST score (I, II, III, IV, V, VI)
- Prior use of botulinum toxin (Naive, Non-Naive)

Subject demographic data will be summarized for the ITT population by treatment group and overall. Age, height, weight, and BMI, will be analyzed as continuous variables. Gender, race, ethnicity, Fitzpatrick skin type, and prior botulinum toxin use status will be analyzed as categorical variables.

Demographics and baseline characteristics will be presented by subject in a data listing.

2.3.4 Medical history and previous/concomitant medication (including drugs and medical and surgical procedures)

All summaries will be done by treatment group based on the ITT population. History of relevant or clinically significant surgical events and medical conditions, including any prior cosmetic/aesthetic procedures or implants, will be collected. Medical History will be coded according to MedDRA; the version used will be noted as a footnote in the tables and listings.

The number and percentage of subjects reporting medical history will be summarized by system organ class (SOC) and preferred term (PT). System organ class and PTs will be presented in descending frequency first based on the QM1114-DP group, and then alphabetically if there are ties. Each subject will contribute at most one count per summarization category. In other words, if a subject has more than one medical history event with same PT, the subject will be counted only once for that PT. Similarly, if a subject has more than one medical history event for a SOC, the subject will be counted only once in that SOC.

Cosmetic/aesthetic procedures and/or implant history will also be presented and will follow the same methods specified above.

Medical history, and prior cosmetic/aesthetic procedures or implants will be provided in the subject data listing. Medical history will be further presented in a separate listing by past and ongoing LCL medical history.

Concomitant medications for this study are defined as any ongoing medications with a start date prior to the date of injection, any changes to existing medications (such as dose or formulation) during the course of the study, or any new medications received by the subject since the date of injection. Prior medications are medications with stop dates prior to study treatment and used within 4 weeks preceding screening visit. Medications will be coded using the World Health Organization (WHO) Drug Dictionary; concomitant procedures will be coded according to MedDRA. The versions used for the coding will be noted as a footnote in the tables and listings.

The number and percentage of subjects who receive prior and concomitant medications will be summarized by the WHO Drug Dictionary Anatomical Therapeutic Chemical 3rd level (ATC-3) and the preferred name. If the 3rd level term is not available, the next available level (e.g., ATC-2)

| | Title 43QM1901 Statistical Analysis Plan US - QM1114-DP - LCL | Doc id |
|----------|--|----------|
| GALDERMA | io Quitto i sumbutum job i ma es Quitti Di Deb | MA-43263 |

Print date:

2021-04-15 15:20

will be used. In addition, the number and percentage of subjects reporting a concomitant medication/therapy will be summarized by reason (medical history, adverse event, concomitant procedure, contraception, or other). Therapies and procedures that started due to an AE will be summarized separately from those who did not start due to an AE.

ATC-3 and preferred name will be presented in descending frequency first based on the QM1114-DP group, and then alphabetically if there are ties. Each subject will contribute at most one count per summarization category. In other words, if a subject has more than one medication with same preferred name, the subject will be counted only once for that preferred name. Similarly, if a subject has more than one medication for an ATC-3 level, the subject will be counted only once in that ATC-3 level and preferred name. Concomitant procedures will also be presented and will follow the same methods specified for medical history.

Prior and concomitant medications/procedures will be presented by subject in a data listing.

Handling of Missing/Partial Dates

While every effort will be made to obtain full, complete information on every reported medication, the following imputation rules will be followed for any respective missing medication data:

For the purpose of determining whether a medication is considered prior or concomitant, the following date imputation rules will used. Dates will be presented as collected in the listings.

Start Date

- If the start date is completely missing, it will be assumed that the medication started on the study treatment date.
- If the start date is missing the day, the first of the month will be used (i.e. UNK-JAN-2019 becomes 01-JAN-2019), provided the imputed date is on or after the subject's study treatment date; otherwise, the day of study treatment will be used.
- If the start date is missing the month, the month of 'June' will be used (i.e. 01-UNK-2019 becomes 01-JUN-2019), provided the imputed date is on or after the subject's study treatment date; otherwise, the subsequent month after study treatment will be used.
- If the start date is missing the year, the year of study treatment will be used (i.e. 01-JAN-UNK becomes 01-JAN-2019), provided the imputed date is on or after the subject's study treatment date; otherwise, the subsequent year after treatment will be used.

End Date

- If the end date is completely missing, it will be assumed that the medication is still ongoing and will not be imputed.
- If the end date is missing the day, the last day of the month will be used (i.e. UNK-JAN-2019 becomes 31-JAN-2019).
- If the end date is missing the month, the subsequent month after the start date will be used.
- If the end date is missing the year, the year of study treatment will be used (i.e. 01-JAN-UNK becomes 01-JAN-2019), provided the imputed date is after the start date, otherwise, the subsequent year after start date will be used.

| | 43QM1901 Statistical Analysis Plan US - QM1114-DP - LCL | Doc id |
|----------|---|----------|
| GALDERMA | | MA-43263 |

Print date:

2021-04-15 15:20

2.4 Efficacy analysis

2.4.1 Datasets analyzed

The primary efficacy analysis will be analyzed based on the mITT population. All secondary variables will be analyzed based on the ITT population, unless otherwise specified below.

2.4.2 Handling of missing data

In general, the number of subjects with missing values will be summarized and reported as appropriate in all outputs. The primary analysis will be performed using multiple imputation (MI) as the primary imputation method and repeated using baseline observation carried forward (BOCF) as a sensitivity analysis for missing values. With the BOCF imputation method, if a subject is missing their Month 1 LCL-ILA score or Month 1 LCL-SLA score, their LCL-ILA/LCL-SLA score at baseline will be used, respectively.

The imputation using MI will assume the Missing Completely at Random (MCAR) missing data assumption. Regardless of the actual pattern of missing data, the Markov Chain Monte Carlo (MCMC) method of the MI procedure from the SAS® system will first be used to create a monotonic pattern of missing data. Then, a second MI procedure will be used to generate five sets of data with missing values imputed from observed data. Linear regressions will be employed to model the missing left LCL-ILA, right LCL-ILA, left LCL-SLA, and right LCL-SLA scores separately, with the following covariates included in each imputation model: treatment group and non-missing LCL-ILA or LCL-SLA data, respectively, from earlier timepoints (baseline, Day 7, and Day 14). The imputed datasets will be used to create the composite responder variable, which will then be analyzed using the methodology described for the primary analysis of responder rates at Month 1 (Section 2.4.3). The results from the analysis of the multiple imputed datasets will be combined by the MIANALYZE procedure of the SAS® system. The seed number to be used will be the number 110198.

The secondary efficacy analysis (described in Section 2.4.4) will be performed using the Observed Cases (OC), that is, no imputation will be done.

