12.1 Protocol Version 3.0 to Version 4.0

Remote assessment procedures for efficacy and safety endpoints to ensure safety and respect localized and elective restrictions were implemented due to COVID-19 pandemic. Therefore, the modified Intention-to-treat (mITT) efficacy population is added to the statistical analyses for primary efficacy analysis. This action affect several sections of the Protocol as summarized below.

Section in the clinical study protocol	Rational for changes	Description of changes
Section 9.1.1, Data Transformations	Clarification	CCI
Section 9.1.2.1, Populations Analyzed and Evaluability; List of abbreviations and definitions of terms	Due to COVID-19 pandemic actions. The mITT efficacy population will be used for assessment of the primary efficacy endpoint. Subjects with a photographic and categorical scale Month 1 assessment via a remote visit will be excluded from the mITT	Modified Intent-to-treat (mITT) Efficacy Population added (primary efficacy analysis).
Section 9.1.2.2, Intent to treat (ITT) Efficacy Population	Due to COVID-19 pandemic actions.	The mITT population will be used for primary efficacy analysis. A sensitivity analysis of the primary efficacy endpoint will be based on the ITT population.
Section 9.1.2.3, Per- protocol (PP) Efficacy Population	Clarification due to COVID-19 pandemic actions.	Changed from "ITT" to "mITT"
Section 9.1.2.5, Imputation of Missing Data	Due to COVID-19 pandemic actions. An increased number of drop-outs/missing data at Month 1 visit.	Primary imputation changed to "MI" instead of "BOCF".
Section 9.1.5, Inferential Statistical Analyses	Clarification due to COVID-19 pandemic actions.	Added: "The analysis of the primary efficacy endpoint will be based on the mITT population. A sensitivity analysis of the primary efficacy endpoint will be performed using the ITT population." "The secondary analysis in the sequence will be based on the ITT population with the remote visit

Trile 43QM1901 Clinical Study Protocol - QM1114 - LCL

Doc id

Print date:

MA-40370

2020-06-11 13:03

Section in the clinical study protocol	Rational for changes	Description of changes
		assessments excluded. A sensitivity analysis will be run using the ITT population including the remote visit assessments."

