2.4.3 Primary analysis

The primary efficacy endpoint will be the composite responder rate based on the LCL-ILA and LCL-SLA of lateral canthal line severity at maximum smile at Month 1 (described in Section 1.3.1 and Section 1.3.2, respectively). To evaluate the effectiveness of QM1114-DP versus placebo in the treatment of moderate to severe LCL, the responder rates of the QM1114-DP and placebo will be compared using the Cochran-Mantel-Haenszel (CMH) test, stratified by site, at the 5% significance level (2-sided).

The null hypothesis of no relationship between treatment and responder rate (i.e. the responder rates are the same in both groups) will be tested against the alternative hypothesis that there is a relationship between treatment and responder rate (i.e. the responder rates are different in the two groups). For a significant result, the two-sided p-value of the comparison of the composite LCL-ILA/LCL-SLA responder rates between the QM1114-DP treated and placebo treated subjects at

Doc id 43QM1901 Statistical Analysis Plan US - QM1114-DP - LCL 👶 GALDERMA MA-43263

Print date:

2021-04-15 15:20

Month 1 using the CMH test needs to be smaller than 0.05. The Breslow-Day test will be used to assess the homogeneity of the odds ratios across all sites.

The estimates of the composite LCL-ILA/LCL-SLA responder rates in each treatment group will be presented as well as the difference in responder rates (QM1114-DP responder rate – placebo responder rate). Corresponding 95% CI for the treatment group composite LCL-ILA/LCL-SLA responder rates and the difference in responder rates along with the p-value for the difference will also be presented. The normal approximation (Wald) method will be used to calculate both the 95% CI for the individual treatment group composite LCL-ILA/LCL-SLA responder rates and the 95% CI for the difference in responder rates. The above responder rates will be presented in figures by visit and treatment group.

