2.7.3 Sample size calculation

The study is planned to include approximately 300 subjects, of whom 225 will be treated with QM1114-DP and 75 subjects will receive placebo.

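### Five imputed datasets leave small but avoidable Monte Carlo error in the primary treatment difference and its confidence limits

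*SAP*

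**What the plan says.** On the primary endpoint, SAP 2.4.2 states: "The primary analysis will be performed using multiple imputation (MI) as the primary imputation method". The work is done in two steps. An MCMC step first makes the missing-data pattern monotone. After that, "a second MI procedure will be used to generate five sets of data with missing values imputed from observed data". Each Month 1 score (left and right, investigator and subject) is modelled by linear regression on treatment group and the earlier scores on the same scale at baseline, Day 7 and Day 14. On pooling: "The results from the analysis of the multiple imputed datasets will be combined by the MIANALYZE procedure of the SAS® system". On the seed: "The seed number to be used will be the number 110198".

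SAP 2.4.3 then reports the difference in responder rates with a 95% Wald interval. The success rule is the two-sided CMH p-value: "Month 1 using the CMH test needs to be smaller than 0.05".

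The documents give no reason for choosing five, set no target for Monte Carlo error, and plan no repeat with another seed or more imputations. They also give no expected missing rate. The amendment summary (Protocol 12.1) only gives the reason for moving to multiple imputation: "An increased number of drop-outs/missing data at Month 1 visit".

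**The concern.** With m imputations, the pooled estimate averages m random draws, and the between-imputation variance B is estimated on m − 1 degrees of freedom. For m = 5 that is 4 degrees of freedom, so the estimate of B has a relative standard deviation of about √(2/4) = 71%, against √(2/99) = 14% for m = 100. B enters the pooled standard error and the t reference, so both the centre and the width of the interval depend on the seed.

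This is the primary analysis of a trial that expects more missing Month 1 data, and the difference with its interval is the headline result. Noise that more computing would remove should not show in it.

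There is a second, smaller point. The number five is attached only to the second step, and the number of MCMC draws at the first step is not given. One possible reading is a single MCMC pass. Intermittent missing Day 7 or Day 14 grades would then be identical in all five sets, and the uncertainty in those draws would be left out.

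**Working it through.** The documents state no power, missing rate or Monte Carlo error for this point, so there is no planned figure to reproduce.

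**Inputs from the documents.** m = 5 and seed 110198 (SAP 2.4.2); two-sided 5% level and Wald interval (SAP 2.4.3). On sample size, SAP 2.7.3 says: "The study is planned to include approximately 300 subjects, of whom 225 will be treated with QM1114-DP and 75 subjects will receive placebo".

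**Assumptions.** Month 1 missing fraction f of 5% to 20%, equal in both arms. Active response 25% to 50% and placebo 2% to 20%, with 45% against 3% as the worked case.

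**Step 1: earlier visits predict nothing (upper bound).**

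- V = p1(1 − p1)/225 + p0(1 − p0)/75
- B = V·f/(1 − f)
- Monte Carlo SD of the pooled difference = √(B/m)

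For 45% against 3%: V = 0.2475/225 + 0.0291/75 = 0.001100 + 0.000388 = 0.001488, a complete-data SE of 3.86 points. At f = 10%, B = 0.001488 × 0.1/0.9 = 0.0001653. With m = 5 the SD is √(0.0001653/5) = 0.57 points; with m = 100 it is 0.13. At f = 20%, B = 0.001488 × 0.25 = 0.000372, which gives 0.86 and 0.19 points.

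Over the whole assumed range of response rates (complete-data SE 3.3 to 5.7 points), m = 5 gives an SD of 0.3–0.6 points at 5% missing, 0.5–0.9 at 10% and 0.7–1.3 at 20%.

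**Step 2: confidence limits in the same case.** Simulation over 2,000 seeds, with beta-binomial imputation within arm, Rubin's rules and t limits, for 45% against 3%. Central 95% of seeds for the lower limit:

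| Missing | m = 5 | Spread | m = 100 | Spread |
|---|---|---|---|---|
| 5% | 33.1–35.1 | 2.0 | 34.1–34.5 | 0.4 |
| 10% | 31.7–35.1 | 3.4 | 33.4–34.1 | 0.7 |
| 20% | 29.2–35.0 | 5.8 | 32.3–33.4 | 1.1 |

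A repeat gave 3.2 and 5.7 points at 10% and 20%. The spread depends on the rates: at 50% against 20% it is 4.7 and 7.9 points.

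**Step 3: a model close to the SAP.** Four Month 1 scores were regressed on treatment and the same-scale baseline, Day 7 and Day 14 scores, and the composite responder was then derived. Imputed scores were rounded to grades 0–3, which is an assumption. Simulated active response was 20% to 52% and placebo about 0.

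| Missing | SD of difference, m = 5 | 95% seed spread of a limit, m = 5 | SD of difference, m = 50 |
|---|---|---|---|
| 5% | 0.16–0.26 | 0.6–1.1 | 0.05–0.08 |
| 10% | 0.22–0.29 | 0.8–1.2 | 0.07–0.10 |
| 20% | 0.31–0.45 | 1.1–2.1 | 0.10–0.14 |

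Separate runs of the same kind gave 0.15–0.5 points for the SD and 0.5–2.6 for the spread of the lower limit. I summarise these as about 0.15–0.5 and 0.5–2.5.

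**Step 4: how much of the drop is due to the covariates.** Part of it comes from the near-zero placebo rate in step 3. With placebo at 0 and active at 35%, V = 0.2275/225 = 0.001011, and the no-covariate SD at 20% missing is √(0.001011 × 0.25/5) = 0.71 points, against 0.45 in step 3. The ratio is 0.63. Applied to the 45%-against-3% case, it gives 0.63 × 0.86 = 0.54 points, still about half a point.

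**Step 5: effect of more imputations.** The Monte Carlo SD of the difference falls by √(100/5) = 4.5 with m = 100, or √(50/5) = 3.2 with m = 50, whatever the missing rate.

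**The case against.** The strongest reply is that nothing here is wrong, and most of it stands. Rubin's rules already add B/m to the variance and adjust the degrees of freedom, so five imputations do not invalidate the interval. The seed is written into the SAP, so the run can be repeated and no favourable seed can be picked later. The error is small against a sampling SE of 3.3 to 5.7 points, and the cost in width is slight: a mean half-width of 8.9 against 8.7 points at 20% missing, without covariates.

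A reader might infer that the headline figures carry random error of several points. The documents do not support that. They give no missing rate, and SAP 2.2 removes subjects with a remote Month 1 assessment from the mITT population, so those visits are not imputed. Spreads of several points appear for the limits when the earlier grades are ignored, and the SAP does not plan to ignore them. In the model close to the SAP, the limits also move little more than the estimate does (SD 0.20–0.32 against 0.22–0.29 points at 10% missing).

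The single-pass reading of the MCMC step is only one reading. The SAP does not say that the step runs once, and the effect has not been quantified.

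What does not stand is the idea that the planned sensitivity analyses cover this. BOCF and the ITT observed-case analysis test the missing-data assumptions; they do not reduce the Monte Carlo error in the primary result.

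**Conclusion.** The point holds as a free improvement. Under an assumed 5% to 20% missing and the planned covariates, five imputations leave a seed-to-seed SD of about 0.15 to 0.5 points in the difference and a 95% seed spread of about 0.5 to 2.5 points in a limit. The spread of about 2 to 6 points applies at 45% against 3% if the earlier visits carry no information. The figures rest on assumed response and missing rates and on a near-zero placebo rate in the closer model.

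A reader might also infer that significance hangs on the seed. That is unlikely for a large effect: in the least favourable row of the step 2 table, the lower limit still starts at 29.2 points. The CMH p-value itself was not simulated, and a small true effect would leave less room.

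**What to change.** In SAP 2.4.2, replace five with a larger number such as 100; 50 would already suffice. State that the MCMC step creates that many monotone datasets and that the second step imputes once within each, so that draws for intermittent missing grades also vary and only one implementation is possible. Keep seed 110198. Reporting the Monte Carlo standard error, √(B/m), beside the pooled difference would show that the remaining noise is negligible.

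The cost is one number, one clause and negligible computing time. Estimand, test and significance level do not change. The change should be made before unblinding. Protocol 9.1 requires any change to the finalised SAP to be documented in the clinical study report.

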In the early 1990s, patients treated with BoNT-A for blepharospasm were observed to lose their frown lines and, ^{5,9} since publishing these observations, the use of BoNT-A in the aesthetic setting has accelerated. Injectable BoNT-A products have been investigated for multiple aesthetic indications in attempts to reverse the appearance of aging, especially in the facial region.² In the treatment of facial lines, the effect of BoNT-A injections usually persists for approximately 4-6 months. Facial muscle activity and severity of the facial wrinkles then returns to baseline. Full functionality of facial muscles is usually restored by approximately 6 months post-treatment. 10

There is one BoNT-A product currently licensed in the US for the treatment of LCL in adults (Botox Cosmetic®). QM1114-DP is a novel botulinum toxin type-A1 which is presented as a liquid formulation. Unlike the main commercially available botulinum toxins in the United States, QM1114-DP is manufactured and formulated without any animal or human proteins. As a novel BoNT-A with a differentiated formulation, QM1114-DP is being developed for the treatment of moderate to severe LCL in adults over 18 years.

GALDERMA

Title
43QM1901 Clinical Study Protocol - QM1114 - LCL

MA-40370

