7. CLINICAL STUDY ASSESSMENT

7.1 Efficacy Assessments

7.1.1 Investigator 4-point Photographic Scale of LCL Severity (LCL-ILA)

The validated Investigator 4-point Photographic Scale of Lateral Canthal Line Severity (LCL-ILA) (Appendix 1), developed by Galderma, includes two grading systems: one for the Investigator live assessments at maximum smile, The scale represents LCL severities from none (grade 0), mild (grade 1), moderate (grade 2), to severe (grade 3). Each grade is also depicted by an individual photograph and descriptive text. The Investigators will be trained on the use of the LCL-ILA.

The Investigators will use the LCL-ILA for direct, live comparison with the subject's face for grading LCL severity at screening, baseline (prior to treatment), and at all post-treatment visits. Left and right LCL should be assessed separately at maximum smile.

Print date:

2020-06-11 13:03

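### The primary Month 1 imputation uses five draws, leaves out site and later grades, and is labelled MCAR: a small, cheaply avoidable loss of precision and reproducibility

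*SAP*

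**What the plan says.** SAP 2.4.2 makes multiple imputation the primary method for missing Month 1 scores and works in two stages. An MCMC "method of the MI procedure from the SAS® system will first be used to create a monotonic pattern of missing data". After that, "a second MI procedure will be used to generate five sets of data with missing values imputed from observed data". The variables in the MCMC stage are not listed, and neither is the number of draws taken there.

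For the second stage, "Linear regressions will be employed to model the missing left LCL-ILA, right LCL-ILA, left LCL-SLA, and right LCL-SLA scores separately", and the covariates are "treatment group and non-missing LCL-ILA or LCL-SLA data, respectively, from earlier timepoints (baseline, Day 7, and Day 14". Site is not among them, although it stratifies the randomisation (SAP 1.1.2) and the CMH test (SAP 2.4.3). On the mechanism: "The imputation using MI will assume the Missing Completely at Random (MCAR) missing data assumption".

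The investigator scale is used for "grading LCL severity at screening, baseline (prior to treatment), and at all post-treatment visits" (Protocol 7.1.1), and Protocol 7.1.2 sets the same schedule for the subject scale. Month 2 and Month 3 grades will therefore exist for a subject who misses only Month 1. The missing-data sensitivity analyses in SAP 2.4.3.1 are BOCF and ITT observed cases. Neither uses later grades.

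Protocol 12.1 explains why multiple imputation replaced BOCF as the primary method: "An increased number of drop-outs/missing data at Month 1 visit", linked to the pandemic.

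**The concern.** The imputed scores feed the composite responder, and through it the primary test and the headline rate. Four features of the model look weaker than they need to be.

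- **Number of draws.** Five draws leave Monte Carlo error in the pooled estimate. The fixed seed (110198) lets the run be repeated, but a different seed would give a different answer.
- **Site.** The analysis stratifies by site, while the imputation treats all sites as alike.
- **Assumption.** Under MCAR, imputation is not needed to remove bias. A model that conditions on treatment and earlier grades is justified under MAR, so the label and the method do not match.
- **Later grades.** Protocol 1.1 says that "the effect of BoNT-A injections usually persists for approximately 4-6 months". A Month 2 grade should therefore say something about Month 1, yet the listed covariates stop at Day 14.

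At stake are the precision and reproducibility of the primary estimate.

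**Working it through.** **Inputs from the documents.** About 300 subjects at 3:1: 300 × 3/4 = 225 active and 300 × 1/4 = 75 placebo, as stated in SAP 2.7.3. There are five imputations. No missing rate, between-visit correlation or Monte Carlo error is given, so there is no planned figure to reproduce, and the values below are assumptions.

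**Step 1: seed dependence.** Assume k = 22 active subjects lack Month 1 (22/225 = 9.8%), with a per-subject imputation variance v of 0.15 to 0.25. Treating the draws as independent, the seed-to-seed SD of the pooled active rate is √(k·v) / 225 / √m.

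- m = 5, v = 0.15: √3.3 / 225 / √5 = 0.0036, or 0.36 points
- m = 5, v = 0.25: √5.5 / 225 / √5 = 0.0047, or 0.47 points
- m = 50: 0.11 to 0.15 points

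For comparison, the sampling SD of a 45% rate (assumed) in 225 subjects is √(0.45 × 0.55 / 225) = 0.033, or 3.3 points. At most, five draws add (0.47/3.3)² = 2% to the variance.

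**Step 2: Month 2 as an extra covariate.** Trials of 225:75 were simulated with four correlated 0-3 scores per visit and response rates of about 36% and 0%. There were 1,500 trials per setting, and m = 5. Each score was imputed by its own Bayesian linear regression and rounded to the nearest grade (an assumed rule). Only Month 1 was missing, so every affected subject had a Month 2 grade, which favours adding it. Results under MCAR, in percentage points of the rate difference:

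| Missing | Shift from complete data, SAP model | Shift with Month 2 | Gap between the two | SD of estimate, SAP / with Month 2 | SD of imputation error, SAP / with Month 2 |
|---|---|---|---|---|---|
| 3% | -0.52 | -0.46 | 0.07 | 3.25 / 3.25 | 0.53 / 0.49 |
| 5% | -0.86 | -0.76 | 0.11 | 3.24 / 3.23 | 0.67 / 0.60 |
| 10% | -1.67 | -1.42 | 0.25 | 3.23 / 3.22 | 0.91 / 0.84 |
| 20% | -3.35 | -2.93 | 0.42 | 3.13 / 3.12 | 1.30 / 1.20 |

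(Gaps were taken before rounding.) Imputation error falls by roughly 8 to 10%, but it is a small part of the total, so the overall SD barely moves. Most of the downward shift remains with Month 2 in the model. Its likeliest source is the separate linear imputation of four ordinal scores with rounding, as simulated. At 20% missing, the shifts without and with Month 2 were -1.66 and -1.47 when missingness depended on Day 14, and -1.40 and -1.51 (no gain) when it depended on Month 2.

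**Step 3: site and the MCAR label.** No size was computed for omitting site. The argument is consistency between the imputation model and the stratified analysis. Relabelling the assumption changes no computed number; it corrects what the analysis claims to rely on.

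**The case against.** A reader might infer that leaving out Month 2 biases the active rate upward, because dissatisfied non-responders skip Month 1. A latent-normal model can produce this. Assume rates of 45% at Day 14 and Month 1 and 40% at Month 2, correlations with Month 1 of 0.6-0.7 for Day 14 and 0.8-0.9 for Month 2, 10% missing, and 85% of those seen at Month 2. If non-responders have 2 to 5 times the odds of missing Month 1, upward bias falls from 1.2-2.7 points to 0.8-2.1 when Month 2 is used. The documents do not support that reading:

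- The bias needs missingness related to outcome beyond the earlier visits. The stated cause of missing data is the pandemic.
- The correlation ordering is assumed. With a month defined as 28 days, Day 14 lies 14 days from Month 1, and Month 2 lies 28 days away. With 0.85 for Day 14 and 0.65 for Month 2, bias moves only from 0.92 to 0.87 points (odds ratio 2) or from 1.88 to 1.77 (odds ratio 5).
- That model imputes from a binary Day 14 stratum. The SAP also uses baseline and Day 7.
- Drop-outs have no Month 2 grade, and subjects assessed remotely at Month 1 are outside the mITT. How many skip a single visit is unknown.
- BOCF is planned. Eligible subjects start at grade 2 or 3, so carrying baseline forward makes each missing subject a non-responder and cannot overstate the active rate.

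These objections stand against a claim of bias. Two others limit the point further. Five draws add at most about 2% to the variance under the Step 1 assumptions. And because the MCMC variables are not listed, it is not certain that a Month 2 grade goes unused: if later visits enter that step, it would fill a skipped Month 1 as a non-monotone gap. That uncertainty is itself a reason to list them.

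The simulation has limits on the other side: it did not test missingness that depends on the Month 1 outcome itself, and it used five draws throughout.

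**Conclusion.** The point holds as a modest improvement to the primary imputation. As written, SAP 2.4.2 accepts avoidable seed dependence of about 0.4 points in the active rate if 10% of Month 1 data are missing, against a sampling SD of about 3.3 points. It leaves out the stratum used in the randomisation and the test, and it names an assumption that does not match its model. In the MCAR simulation, later grades would recover a further 0.1 to 0.4 points at 3 to 20% missing, with almost no change in overall SD. The missing rates, response rates, correlations and rounding rule are all assumed. On these figures the primary conclusion is unlikely to change. A benefit for bias remains possible but conditional on outcome-related missingness, which the documents do not show.

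**What to change.** Amend SAP 2.4.2 as follows.

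1. Use at least 50 imputations, each built on its own first-stage MCMC draw.
2. Add site to the imputation model, pooled as for the CMH test (SAP 2.1.2).
3. State the assumption as MAR.
4. Add on-site Month 2 and Month 3 grades as auxiliary variables, and list every variable in the MCMC step, so that it is clear which step fills a skipped Month 1. For this purpose, set to missing any remote Month 2 or Month 3 grade, in line with the exclusion of remote assessments in SAP 2.2 and 2.4.4, and any grade after a prohibited treatment (Protocol 5.4.5). Without this rule, data that the plan excludes elsewhere could re-enter the primary analysis.

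Baseline, Day 7 and Day 14 stay in the model, and BOCF stays as the conservative check. The cost is SAP wording and a few lines of SAS, with no new data collection. The downside is a slightly larger imputation model and some pooling of small sites.
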